**I. Hypotheses (H) and Specific Aims (SA):**

[figure not shown]
Over 1.25 million Americans have type 1 diabetes (T1D), increasing risk for early death from cardiorenal disease (1, 2). Despite advances in glycemic and blood pressure control, a child diagnosed with T1D is expected to live up to 17 years less than non-diabetic peers (3-6). The strongest risk factor for cardiovascular disease (CVD) and mortality in T1D is diabetic kidney disease (DKD) (7, 8). Current treatments, such as control of hyperglycemia and hypertension, are beneficial, but only partially protect against DKD. Clinical trials in DKD have yielded disappointing results (9-16), potentially due to the lack of interventions at early stages of disease when the benefit is most likely. In fact, the recently published results from the AdDIT trial demonstrated that use of angiotensin converting enzyme inhibitor (ACEi) and statin failed to change albumin excretion over time in youth with T1D (17). Thus, identifying new therapies to impede DKD remains a public health priority.

Hyperfiltration is common in youth with T1D (18, 19), and predicts progressive DKD. Hyperfiltration is also associated with early changes in intrarenal hemodynamic function, including increased effective renal plasma flow (ERPF) and glomerular pressure. **Figure 1** summarizes the changes in glomerular filtration rate (GFR) and ERPF, that we propose underlie the natural history of DKD in T1D. Intrarenal hemodynamic function is strongly influenced by the renin–angiotensin–aldosterone system (RAAS) system, which is also considered a key player in the pathogenesis of DKD. In particular, angiotensin II (Ang II), shows increased activity during DKD (20, 21). Our preliminary data demonstrate differences in intrarenal hemodynamic function and RAAS activation in early and advanced DKD in T1D (22,23). The pathophysiology contributing to the differences observed in RAAS activation and intrarenal hemodynamic function in T1D are poorly defined.

Animal research demonstrates that arginine vasopressin (AVP) acts directly at the V2 receptor (V2R) to modify intrarenal hemodynamic function (24), but also indirectly by activating RAAS (22) (**Fig 2**). Our preliminary data suggest that elevated copeptin, a marker of AVP, predicts DKD in T1D adults, independently of other risk factors (25, 26). However, no human studies to date have examined how copeptin relates to intrarenal hemodynamic function in early DKD in T1D. A better understanding of this relationship is critical to inform development of new therapies targeting the AVP system in T1D. Accordingly, in this application, we propose to define the relationship between copeptin and intrarenal hemodynamics in early stages of DKD, by studying youth aged 12-21 y with T1D duration < 10 y (**Fig. 1**).

**Fig. 2**

**SA1: Define the relationship between copeptin and intrarenal hemodynamic function in T1D youth.**

[figure not shown]
H1.1: Copeptin will be higher in youth with T1D and hyperfiltration vs. those without hyperfiltration.

H1.2: Copeptin will *positively* correlate with GFR, ERPF and intrarenal hemodynamics in short-standing T1D.

**SA2: To understand the effects of copeptin on renal oxygenation and perfusion in T1D youth.**

H2.1: Copeptin will correlate positively with renal oxygenation consumption and perfusion in T1D youth.

**II. Background and Significance:** Prior bench and translational research into the mechanisms of hyperglycemic injury and its modifiers (27) has to date not successfully translated into adjuvant therapeutics to supplement intensive insulin therapy in the prevention of DKD. Accordingly, there is an urgent need for novel modifiable risk factors. AVP has diverse actions in physiology which include direct effects on vascular hemodynamics, RAAS, volume, and osmolality regulation (28, 29). The actions of AVP are mediated by at least three distinct receptor subtypes: V1a, V1b, and V2. Experimental data strongly support a causal and direct role of AVP in the pathogenesis of kidney disease through V2R activation (30, 31) (Fig 3). In laboratory animals, elevated AVP directly leads to afferent arteriolar vasodilation by V2R stimulation (24) and indirectly to efferent arteriolar constriction by RAAS activation (28, 29). The net effects are increased ERPF with glomerular hypertension and hyperfiltration (Fig 3), in addition to albuminuria and tubulopathy (32-34). Supraphysiologic increases in ERPF, glomerular pressure and GFR are hallmarks of hyperfiltration (35), an early phenotype of DKD which predicts rapid GFR decline and impaired GFR in adults with T1D (36). Measuring AVP is cumbersome due to its small size and short half-life. Copeptin, a more stable peptide derived from the same precursor molecule as AVP, is thus recently recognized as a better method to determine AVP activity and hence will be used in this proposal (33).

**Scientific Premise:** The relationships we and others have demonstrated between copeptin, DKD in T1D are based on epidemiologic data and limited to adults with advanced DKD (25, 26, 37). These studies have established that copeptin is significantly higher in adults with T1D, and that elevated levels of copeptin are associated with cardiorenal disease. Yet no human studies have examined the mechanisms whereby elevated AVP activity contributes to DKD, nor whether this relationship is different in early DKD. Intrarenal hemodynamic function is compromised in both early and advanced DKD (35, 38-40), and recent studies have also provided compelling evidence that intrarenal hemodynamic dysfunction can be partially restored with therapeutic agents in T1D (41-51). However, no data exist on the interaction between copeptin, intrarenal hemodynamic function in early DKD in T1D. Until this gap is addressed, our understanding of AVP as a risk factor and therapeutic target in DKD is limited.

**Our overall hypothesis** is that elevated copeptin in T1D is associated with distinct changes in intrarenal hemodynamic function in early vs. advanced DKD, which includes increased ERPF and GFR in early DKD (e.g. hyperfiltration) and reduced ERPF and GFR in established DKD (e.g. impaired GFR). To test these hypotheses, we will carry out a cross-sectional study in youth with short-standing T1D as well as take advantage of unique mechanistic data already collected in adults with longstanding T1D, with and without advanced DKD (DKD and DKD Resistors) from the JDRF-funded *Canadian Study of Longevity in Diabetes (Longevity)*.

**Impact:** This proposal seeks to investigate the roles of AVP on intrarenal hemodynamic function in youth and adults with early and advanced DKD. By understanding the interplay between AVP and intrarenal hemodynamic function in T1D, we will provide a foundation for future mechanistic studies and clinical trials targeting the AVP system. Renal physiology studies are required to advance DKD research and direct the development of new therapies to improve cardiorenal health and mortality for the growing number of people afflicted by T1D (52).

Our proposal is innovative because:

[figure not shown]
1. **We move beyond** the traditional determinants of DKD (**ABC risk factors**; HbA1c, **Blood pressure** and **LDL-Cholesterol**), to focus on elevated AVP activity.
2. We can validate our epidemiologic findings in CACTI and the T1DX with mechanistic renal physiology data.
3. **Hyperfiltration is understudied.** It is important to examine early changes in GFR, because albuminuria does not reliably reflect progressive DKD and commonly reverts to normoalbuminuria (53). Hyperfiltration is now recognized to be a common phenotype of early DKD in young adults with T1D (18, 19). Hyperfiltration

predisposes to progressive nephron injury by increasing glomerular pressure (54). We have shown that hyperfiltration precedes albuminuria and predicts rapid GFR decline and chronic DKD in adults (36). 4. We propose innovative methods by a highly skilled, multi-disciplinary team to define intrarenal hemodynamic function, including gold standard measurements of GFR by iohexol clearance, ERPF by para-aminohippurate (PAH) clearance and calculations of intrarenal hemodynamic parameters by Gomez' equations (55). 5. There is the potential to translate the findings of these studies to a rational intervention strategy in T1D using selective V2R blockers (e.g. vaptans), which are FDA approved in adults with clinical hyponatremia.

### III. Preliminary Studies/Progress Report:

1. Copeptin concentrations are greater in adults with T1D compared to non-diabetic controls: Copeptin was greater in participants with T1D compared to those without (geometric mean, 95% CI: 3.5 [2.3-3.8] vs. 2.8 [2.7-3.1] pmol/L,  $p=0.003$ ), and the difference remained significant after adjusting for age, sex and eGFR ( $p=0.0008$ ) (26).

Fig 4. Copeptin is higher in DKD

2. Men with T1D and albuminuria have 3-fold higher copeptin levels than men with T1D and normoalbuminuria: In a case-control study from the T1DX Biobank registry, men with T1D and albuminuria (T1D DKD) had greater copeptin levels than men with normoalbuminuria (T1D N). The difference between T1D DKD and T1D N remained significant after adjusting for HbA1c, eGFR and ACEi / angiotensin II receptor blockers (ARB) use (Fig 4). Higher copeptin levels conferred greater odds of impaired GFR, independent of other important risk factors. In a generalized linear mixed model, one standard deviation (SD) increase in copeptin predicted greater odds of impaired GFR (OR: 2.94, 95% CI 1.39-6.21), and remained significant after multivariable adjustments (T1D duration, ACEi/ARB use, HbA1c and case/control status) (25).

3. Copeptin is associated with cardio-renal disease in adults with T1D: In adults with T1D in the CACTI study, elevated copeptin ( $>13$  pmol/L [ $>97.5^{\text{th}}$  percentile for healthy adults]) was associated with greater odds of impaired eGFR (OR: 18.52, 95% CI 4.03-85.02), albuminuria (OR: 10.55, 95% CI 2.24-49.62), and CAC scores  $\geq 300$  (OR: 6.24, 1.51-25.90) adjusting for age, sex, HbA1c, systolic BP and LDL-C (26).

4. Stimulation of the V2R with desmopressin is associated with glomerular and tubular injury: We showed that the administration of desmopressin (des), a V2 agonist, to mice resulted in glomerular and tubular damage. Urine albumin concentration was greater in mice exposed to des (Fig 5). Urinary NGAL excretion was also highest in groups receiving des (30). We next stained tissues for angiotensin converting enzyme (ACE) as a marker of the proximal tubular injury. A progressive loss of ACE was associated with the addition of des (Fig 6). These data support glomerular and tubular injury in response to V2R stimulation (30).

5. Hyperfiltration is common in youth and adults with T1D, and predicts rapid GFR decline and impaired GFR: We demonstrated that the prevalence of hyperfiltration in youth with T1D can exceed 50% when GFR is measured by inulin clearance (56), and between 13-31 % when GFR is estimated by serum creatinine and serum cystatin C (19, 57). The discrepancy in prevalence is likely attributed to the inaccuracy of estimated GFR in the normal to elevated GFR range (44), hence we propose to measure GFR in this study. In adults with T1D (n=646) in CACTI, we also demonstrated that hyperfiltration predicted greater odds of rapid GFR decline over 6-years (OR: 5.00, p<0.0001), when adjusting for traditional risk factors including HbA1c, SBP, LDL-C,

Fig 5. V2R Stimulation - Glomerulopathy

[figure not shown]
[figure not shown]

[figure not shown]
Fig 6. V2 stimulation - Tubulopathy

sex, duration and albumin-to-creatinine ratio (ACR) (58). Furthermore, over 12-year follow-up in CACTI, adults with T1D who experienced rapid GFR decline (annual GFR loss  $> 3\text{mL/min}/1.73\text{m}^2$ ) were more likely to demonstrate hyperfiltration at baseline (OR: 32.9,  $p<0.0001$ ) and impaired GFR at 12-year follow-up (OR: 11.6,  $p=0.0003$ ) (unpublished data). In a parallel analysis we conducted in CACTI and Pittsburgh Epidemiology of Diabetes Complications Study (EDC), elevated GFR at baseline was associated with greater odds of rapid GFR decline over 6 and 8-years respectively (CACTI: OR 2.62,  $p<0.0001$ , EDC: OR 2.16,  $p=0.0003$ ) (59).

## 6. Unique intrarenal hemodynamic dysfunction in early vs. established DKD:

**a. Early DKD in young adults:** We evaluated intrarenal hemodynamic function in healthy controls (n=30, mean age 27) and in normotensive, normoalbuminuric participants with T1D and either normofiltration (n=36, mean age 24, GFR 90–134 ml/min/1.73m^2) or hyperfiltration (n=32, mean age 23, GFR $\geq 135\text{ ml/min}/1.73\text{m}^2$ ) during euglycemic and hyperglycemic conditions. We used Gomez's equations to derive renal blood flow (RBF), efferent ( $R_E$ ) and afferent ( $R_A$ ) arteriolar resistances, glomerular hydrostatic pressure ( $P_{GLO}$ ) from inulin (GFR) and PAH (ERPF) clearances, plasma protein and estimated ultrafiltration coefficients ( $K_{FG}$ ). Participants with T1D and hyperfiltration (T1D-H), had significantly greater GFR, ERPF, RBF, and lower  $R_A$  and higher  $P_{GLO}$  compared to healthy controls (HC) (60) (Fig 7). These observations illustrate the potential of applying Gomez' equations in DKD research.

**Fig 7.** Intrarenal hemodynamics estimated by Gomez's equations in normal healthy controls (HC), and patients with T1D, renal normofiltration (T1D-N) and hyperfiltration (T1D-H) according to sex. \* $P<0.001$  vs. HC, § $P<0.001$  vs T1D-N

In summary, our preliminary epidemiologic data suggest that: 1) copeptin is higher in adults with T1D compared to their non-diabetic peers; 2) elevated copeptin is associated with DKD in the form of albuminuria and impaired GFR, as well as with coronary artery calcification (CAC) in adults with T1D; 3) men with T1D and albuminuria have 3-fold greater copeptin levels than men with T1D with normoalbuminuria; 4) stimulation of V2R with desmopressin (vasopressin agonist) induces tubular and glomerular injuries in murine models; 5) hyperfiltration is common in youth and adults with T1D and predicts rapid GFR decline and impaired GFR; 6) there are unique intrarenal hemodynamic dysfunction profiles in early and advanced DKD in people with T1D, arguing for dedicated studies at different time points in the natural history of DKD. To understand the pathogenesis whereby elevated AVP activity contributes to DKD, we need carefully designed translational studies, like the one proposed in this application, to define the interplay between AVP activity and intrarenal hemodynamic dysfunction in early DKD. The proposed study is feasible in the current environment: 1) the Barbara Davis Center for Diabetes (BDC) and the Anschutz Medical Campus (AMC) provide ample study participants for a study in youth with short-standing T1D; 2) the experience and expertise of the investigator and collaborator team will ensure the success of the planned research.

## IV. Research Methods:

**Study design and study population:** We propose to address SA1 and SA2 with a cross-sectional observational study with 50 youth with short-standing T1D (50% female, 12-21 yr,  $<10$  yr duration). The participants will be recruited from the BDC Clinic (>4000 pediatric patients). Following a screening visit, eligible participants (**Table 1**) will be asked to refrain from strenuous physical activity for 3 days prior to admission due to the impact of exercise on

**Table 1: Eligibility Criteria**

Inclusion criteria	Exclusion criteria
Antibody+ T1D with $<10$ yr duration	Severe illness, recent DKA
Age 12-21 years	ACEi, ARB, diuretics, SGLT 2/1 blockers, atypical antipsychotics, steroids
BMI $\geq 5\text{ percentile}$	Macroalbuminuria ( $>300\text{mg/g}$ ) or eGFR $<60\text{ml/min}/1.73\text{m}^2$
Weight $<300$ lbs.	Pregnancy, nursing
HbA1c $<12\%$	Anemia or allergy to shellfish or iodine
BP $< 140/90\text{ mm Hg}$	

intrarenal hemodynamic function. They will also be provided with a 3-day diet instructions (45% carbohydrates, 30% fat, 25% protein and a goal of 3.45 g salt/day), with females studied in the follicular phase of the menstrual cycle where possible to limit impacts of nutrient and menstrual hormone variations on IR and renal function, as previously described (61). Participants will ask to administer their long

acting insulin (e.g. Lantus or Levemir) like they normally would. Patients on insulin pumps can remain on their basal rate throughout the study. If on a hybrid-closed loop (artificial pancreas), participants will be asked to open their loop for the duration of the study. The morning of the study, participants will be asked to check their blood sugar prior to arriving at the CTRC. If their blood sugar is  $\geq 250$  mg/dL, they will be asked to administer a bolus of short acting insulin using their home correction factor with a blood sugar target of 200 mg/dL.

Participants will arrive the evening before, or present fasting in the morning and have 2 IVs placed and have their blood glucose concentrations clamped in the mild hyperglycemic range (details below) (Fig 8). Baseline blood will be drawn for serum copeptin, lipids, insulin, cystatin c, creatinine, sodium, hematocrit and total protein, and iohexol and PAH boluses given via IV (see below for details). GFR and ERPF will be measured by iohexol and PAH clearance in plasma. A 4 hr urine sample will be collected to calculate ACR and AER.

**Specific methods:** Outcomes are summarized in **Table 2**. Detailed methods are listed below:

**Figure 8 Study Protocol for SA 1**

[figure not shown]

Table 2 – Aims 1 and 2	
Primary Outcomes	Measurement Tool
Copeptin	ThermoFisher Kryptor Plus
GFR	Iohexol clearance
ERPF	PAH clearance
Renal O 2	BOLD-MRI
Renal perf.	ASL-MRI
Secondary Outcomes	
RVR	MAP/RBF (Table 3)
eGFR	Creatinine, cystatin C
Albumin excretion	Albumin-to-creatinine ratio (ACR)

**Hyperglycemic insulin clamp:** One IV will be placed in each arm to clamp the blood glucose concentrations between 170-190 mg/dL. One IV will be used to administer the boluses of iohexol and PAH in addition to a variable infusion of 20% dextrose and insulin, and the other IV will be used for blood draws. Blood glucoses will be measured every 10 minutes at the bedside, and glycemic control will be achieved using the modified and simplified insulin clamp methodology to remove glycemic effects on GFR and ERPF. The rate of insulin is adjusted based on blood specimens drawn every 10 minutes (example algorithm). Patient blood glucose (BG) levels will be checked at 8am, and adjusted to reach and maintain mild hyperglycemia up until 10am. If participant BG <70mg/dl, we will give 4 oz juice and re-test BG in 15 min. If still <70mg/dl, another 4 oz juice will be given, and BG will be re-tested 15 min later. If still <70 mg/dl,

study MD will be called, and IV D20 will be started at 100ml/hr. For BG between 70-180 mg/dL, a variable D20 infusion will be given on a sliding scale based on participant current BG and weight, as used in previous and current studies (COMIRB #13-0122, #16-1752, #18-0704). Once BG  $> 190$ mg/dl, D20 will be discontinued. If BG is not responding to changes within 2 hours or if increases above 200 mg/dl, a study physician will be contacted. Each time blood is drawn during the clamp, blood will be drawn to a clear line in the syringe to ensure there will be no IV fluid dilution and will be re-infused into the subjects after obtaining the blood sample to minimize blood loss. A blood glucose range of 170-190mg/dL (mild

hyperglycemia) was chosen to limit the acute effects of severe hyperglycemia on GFR and ERPF reproducibility, while allowing us to assess renal function in a glycemic milieu similar to the participants native

pathophysiology. Furthermore, the clamp maintains an easily achieved and safe range of glycemia. Co-I [name] has extensive experience with normoglycemic, hyperinsulinemic, hyperglycemic and hypoglycemic clamps in T1D youth, which are well tolerated in the proposed ages.

Iohexol clearance (GFR) and PAH clearance (ERPF): A bolus of iohexol (5mL of 300 mg/ml iohexol [Omnipaque 300, GE Healthcare]) will be given slowly over 2 min followed by a 10 ml normal saline flush, which will be time 0 for the iohexol clearance. 120 min will be allowed for equilibration of iohexol per or local protocol (62, 63). Blood for iohexol clearance will be drawn at +120, +150, +180, +210 and +240 min (62, 63). PAH (weight/75 x 4.2 ml) [University of Minnesota] will be given slowly over 5 minutes followed by a 10 ml normal saline flush. An infusion mixture of 8 mL of PAH and 42 mL of normal saline will be prepared in a 60mL syringe and infused in Syringe Pump at a rate of 24mL/hr, which will be time 0 of the PAH clearance. Ninety min will be allowed for equilibration of PAH per co-investigator [name] protocol (62, 63). Blood for PAH clearance will be drawn at +90 and +120 min (33-36) (Fig 9). We will use Gomez' equations to calculate parameters of intrarenal hemodynamics (56, 64) (Table 2, pg. 5). Hyperfiltration by measured GFR (iohexol) will be defined as  $\geq 135 \text{ ml/min}/1.73\text{m}^2$  (23, 65-67).

The iohexol and PAH infusion period lasts 240 minutes and will occur concurrently with the mildly hyperglycemic clamp during which time the subject will rest in bed in the pediatric CTRC. During the entire 240-minute glucose/insulin infusion period, a pediatric CTRC nurse will remain at the bedside, and a Study Physician or Pediatric Nurse Practitioner or Pediatric Physician Assistant will also remain at the bedside to minimize any risks associated with iohexol and PAH infusion. The IV site will be continuously monitored to minimize risk of IV infiltration.

De-identified coded blood samples will be sent to collaborator [name] lab at NIH/NIDDK who will run iohexol and PAH clearance on a HPLC platform.

RVR and Gomez equations (Table 3): RVR will be calculated as  $\text{RVR} = \text{MAP}/\text{RBF}$ . To derive additional information about intrarenal hemodynamic function we will use mathematical equations by Gomez et al (55). By using measurements of GFR, RBF, ERPF, renal vascular resistance, hematocrit and serum protein, we can calculate afferent and efferent arteriolar resistance ( $R_A$  and  $R_E$ ), glomerular pressure ( $P_{GLO}$ ) and filtration pressure (Table 3).

Albumin excretion: ACR and AER be determined from 4 hr. urine collection.

Copeptin: Copeptin will be measured by ultrasensitive assays on KRYPTOR Compact Plus analyzers using the commercial sandwich immunoluminometric assays (Thermo Fisher Scientific, Waltham, MA). The copeptin assay has a lower limit of detection of 0.9 pmol/L, and a sensitivity of <2pmol/L. Elevated copeptin will be defined as  $>13 \text{ pmol/L}$ , which is  $>97.5^{\text{th}}$  percentile for healthy adults (68).

Estimated GFR: As an exploratory aim, we will evaluate the agreement between measured GFR (iohexol) with estimated GFR by serum creatinine and cystatin C. Due to the expected normal to elevated GFR for youth with T1D, we will calculate eGFR by Zappitelli equation ( $\text{eGFR} = 25.38 * (1/\text{serum cystatin C})^{0.331} * (1/\text{serum creatinine})^{0.602} * (1.88 * \text{height})$ ) (69-71).

[figure not shown]

Table 3 Measures	Definition:
Filtration fraction (FF)	$\text{FF} = \text{GFR} / \text{RPF}$ (renal plasma flow)
Renal blood flow (RBF)	$\text{RBF} = \text{RPF} (1-\text{Hct})$
Renal vascular resistance (RVR)	$\text{RVR} = \text{MAP}/\text{RBF}$
Filtration pressure $\Delta P_F$	$\Delta P_F = \text{GFR}/K_{FG}$ , $K_{FG}$ : filtration coefficient
Mean plasma protein ( $C_M$ )	$C_M = \text{total protein} / \text{FF} \times \text{natural log} (1/1-\text{FF})$
Glomerular oncotic pressure ( $\pi_G$ )	$\pi_G = 5 \times (C_M - 2)$
Glomerular pressure ( $P_{GLO}$ )	$P_{GLO} = \Delta P_F + P_{BOW} + \pi_G$ , $P_{BOW}$ is 10 mmHg
Afferent arteriolar resistance ( $R_A$ )	$R_A = [(MAP - P_{GLO})/\text{RBF}] \times 1328$
Efferent arteriolar resistance ( $R_E$ )	$R_E = [(GFR/K_{FG} \times (RBF-GFR))] \times 1328$

Blood pressure: After participants have been laying supine for a minimum of 5 minutes, blood pressure measurements will be obtained using an automatic blood pressure machine and 3 measurements will be averaged. MAP will be calculated from the blood pressure readings.

Metabolomics: We will measure serum metabolomics by Q Exactive UHPLC-MS Analysis at the Metabolomics Core Facility Services at University of Colorado ([name] [name], PhD).

Urine and serum osmolality: We will directly measure urine and serum osmolality using freezing point method with Micro-Osmometer Model 3300 (Advanced Instruments, Massachusetts, USA) at [name]'s Lab.

Fractional excretion of sodium (FeNa): We will measure serum and urine sodium and creatinine to calculate fractional excretion of sodium.

DXA: Participants will also undergo DXA by standard methods on a Hologic device (Waltham, MA) to determine lean and fat mass (72).

Renal oxygenation and renal perfusion by MRI: The primary outcomes of Aim 2 are renal oxygenation and perfusion (**Table 2**). We will perform BOLD MRI (73) to quantify renal oxygenation, whereas renal perfusion will be measured by ASL (74)(**Table 2**). These studies will be performed at the UCD Research Imaging Center (3T Siemens Skyra scanner) which already has an active renal BOLD-MRI protocol as part of the multi-center COMBINE (CKD Optimal Management with Binders and Nicotinamide) study (**Table 4**) (75), for which our collaborator [name] directs the CORE for trouble-shooting and analyzing the renal MRIs. [name] is an international leader in advanced MR research and will provide the techniques for BOLD and ASL MRI acquisition and analyses.

[figure not shown]
Table 4. MRI protocol_3T Skyra				BOLD	ASL
Series	Localizer				
Plane	2 Plane	Coronal	Axial	Coronal	Coronal
Pulse sequence	gre	gre	gre	gre	Custom
TR/ms	7	7	7	61	3000
TE/ms	2.66	2.66	2.66	4.92, 9.84, 14.76, 19.68, 24.6, 29.52, 34.44, 39.36	1.92
Read out mode	n/a	n/a	n/a	Bipolar	n/a
In line mapping	n/a	n/a	n/a	T2* (VB 17)/R2* (VD 13) Map	n/a
BW Hz/pixel	290	290	290	260	501
FOV mm	400	400	400	400	400
Slices	3 ax, 3 cor	5	5	5	1
Concatenation	6	5	5	5	1
Slice Thickness / mm	8	8	8	5	8
Skip	50%	50%	50%	0	n/a
Fat suppressed	No	No	No	Fat Sat	n/a
Parallel Imaging acceleration factor	None	None	None	None	None
Diffusion mode	n/a	n/a	n/a	n/a	n/a
B value s/mm 	n/a	n/a	n/a	n/a	n/a
Diff. gradients	n/a	n/a	n/a	n/a	n/a
NEX	2	2	2	1	50
Acq-matrix	154x256	154x256	154x256	192x256	128x128
Flip angle/degrees	20	20	20	30	60
Typ. Scan time m:s	0:14	0:07	0:07	0:30-1:00 (5 slices)	0:05

Options/commnts	Site preference	Instruct subjects to not to take deep breaths	Changing FOV and/or matrix size not preferred	Instruct subjects to not to take deep breaths.
-----------------	-----------------	---	---	---

**Abbreviations:** BOLD: Blood oxygen level dependent, SSFP: steady state free precession, VLA: vertical long axis view, LVOT: left-ventricular outflow tract view, GRE: gradient recalled echo.

**Recruitment:** Ultimately 50 youth with T1D (50% male) will be enrolled (see power analysis). Recruitment will begin year 1 and will consist of adolescent patients with type 1 diabetes from the Barbara Davis Center for Childhood Diabetes (BDC), where principal investigator [name] and co-investigator Drs. [name] and [name] are medical providers and have weekly clinics. The investigator team has excelled when recruiting adolescent T1D patients. There are almost 4000 pediatric patients actively followed at BDC, and we do not foresee any difficulties with recruitment.

**Detailed Study Visit Descriptions:** The study timeline for is illustrated in **Fig 10**, and details from each study visit is summarized below. Visit 1 is the screening visit and visit 2 and 3 will occur consecutively.

**Visit 1 (Screening visit):** Prescreening will be done by phone or in conjunction with a clinical diabetes visit. The full screening visit will include the consent process, history, allergies confirmed, physical exam, and screening labs (HbA1c, hemoglobin and hematocrit [H&H], serum creatinine, urine microalbumin to creatinine ratio). All females will also have a pregnancy test and detailed menstrual history. The screening visit will take approximately 2 hours.

**Visit 2, part 1:** Participants will present the evening before the study visit, or present fasting to the Pediatric CTRC in the morning, and have IV(s) placed. Fasting blood will be drawn for serum copeptin, lipids, insulin, cystatin c, creatinine, sodium, hematocrit and total protein prior to the clamp. Participants will be escorted to the Brain Imaging Center or CHC Radiology for a BOLD and ASL MRI per local protocol. BOLD MRI measurements will be performed at baseline and following administration of a small dose of furosemide (20 mg IV) via the PIV. A study physician or nurse will be responsible for the furosemide administration. Total duration of part 1 will be approximately 1.5 hours.

**Visit 2, part 2:** Participants return to pediatric CTRC and will have their blood glucose concentrations clamped in the hyperglycemic range. Participants will also undergo iohexol and PAH clearance studies, in addition to 4-hour urine collection for album excretion rate (AER) and albumin to creatinine ratio (ACR). Upon completion of visit 2, participants will be provided with a study meal (lunch). After lunch, participants will undergo DXA scan for quantification of body composition. This concludes the study. Total duration 6 hours.

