## G. Data Analysis Plan (formulated with biostatistician [name] PhD):

### ***Aim 1 - Power calculations, statistical analysis, rigor and reproducibility:***

Primary outcomes for Aim 1 and study groups to be compared are summarized in **Table 8**. Based on our and others preliminary data we expect that 40% of youth with T1D (12-21 y) will demonstrate hyperfiltration (GFR

$\geq 135 \text{ ml/min/1.73m}^2$ ). Thus, a sample size of 50 youth with T1D provides 80% power to detect difference of 6.4 pmol/L in copeptin concentration between youth with T1D with and without hyperfiltration (H1.1), and 80% power to detect a correlation of 0.38 between copeptin, GFR and ERPF in youth with T1D (H1.2). Continuous variables will be checked for the distributional assumption of normality using plots. Variables that are skewed will be natural log-transformed for analyses. Descriptive statistics will be used to summarize baseline participant characteristics. Univariable and multivariable linear regression models will be built to examine the relationships between copeptin, GFR, ERPF and calculated intrarenal hemodynamic parameters (derived by Gomez' equations). Variables considered for inclusion in the multivariable models will include: age, sex, ethnicity, pubertal staging, BMI and HbA1c. A P-value  $< 0.05$  will be considered statistically significant. Analyses will be performed in SAS (v9.4; SAS Institute, Cary, NC).

Table 8 – Aim 1

Primary Outcomes:	Groups:
GFR and ERPF	T1D w/ hyperfiltration vs. T2D w/o hyperfiltration

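### Table 3 multiplies renal plasma flow by (1 − Hct) where it should divide, so RBF, RVR, R_A and R_E are wrong by a factor that varies with haematocrit

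*Combined protocol and SAP*

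**What the plan says.** In section IV, Research Methods, the paragraph on RVR and the Gomez equations says: "By using measurements of GFR, RBF, ERPF, renal vascular resistance, hematocrit and serum protein, we can calculate afferent and efferent arteriolar resistance". Table 3 gives the definitions. The rows that matter here are:

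- **RBF:** RPF times (1 − Hct), printed as a product.
- **RVR:** MAP divided by RBF.
- **R_A:** MAP minus P_GLO, divided by RBF, times 1328.
- **R_E:** "R_E = [(GFR/K_{FG} \times (RBF-GFR))] \times 1328".
- **P_GLO:** "P_{GLO} = \Delta P_F + P_{BOW} + \pi_G", which contains no RBF term.

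Table 2 lists RVR first among the secondary outcomes and defines it by pointing to Table 3. The Aim 1 analysis in section G regresses copeptin against GFR, ERPF and the "calculated intrarenal hemodynamic parameters". No other part of the document gives a different formula for RBF.

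**The concern.** Haematocrit is the cell fraction of blood, so plasma is the fraction 1 − Hct. Hence RPF = RBF × (1 − Hct), and RBF = RPF/(1 − Hct). Table 3 has this the wrong way round. Whole-blood flow then falls below plasma flow at any haematocrit above zero, which is impossible.

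A constant scale error would leave every correlation and regression test unchanged. This error is not constant. It depends on each participant's haematocrit, which differs by sex and hydration. Half the sample is to be female. The Background section describes vasopressin as a regulator of volume and osmolality, so some link between copeptin and haematocrit is plausible. Haematocrit is not among the Aim 1 candidate covariates, and univariable models are planned.

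The Aim 1 expected-outcomes text predicts a positive copeptin–RVR correlation. If copeptin rises with haematocrit, the printed formula pushes the estimate towards that prediction, while the correct formula pushes it the other way.

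The R_E row has a second fault. By the table's own filtration-pressure row, GFR/K_FG is a pressure. The row multiplies it by the flow RBF − GFR, whereas RVR and R_A in the same table are pressures divided by flows.

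**Working it through.** The plan states no RBF or resistance value to reproduce, and none of its power figures depends on RBF. The check is therefore algebra on Table 3.

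**Inputs.** GFR 135 ml/min/1.73m² is the hyperfiltration threshold in section IV. FF 17.7% is the alternative threshold in the Aim 1 expected-outcomes text. Together they give RPF = 135/0.177 = 763. The documents give no haematocrit figure, so 0.35 to 0.45 is assumed.

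**Error factors (printed ÷ correct).**

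- RBF: RPF(1 − Hct) ÷ [RPF/(1 − Hct)] = (1 − Hct)².
- RVR and R_A: both are inversely proportional to RBF, and P_GLO does not use RBF, so the factor is 1/(1 − Hct)².
- R_E, taking RBF − GFR as the divisor: [1/(1 − Hct) − FF] ÷ [(1 − Hct) − FF]. This depends on FF as well as Hct.

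| Hct (assumed) | RBF printed | RBF correct | RVR, R_A factor | R_E factor (as quotient) |
|---|---|---|---|---|
| 0.35 | 496 | 1173 | 2.37 | 2.88 |
| 0.40 | 458 | 1271 | 2.78 | 3.52 |
| 0.45 | 419 | 1387 | 3.31 | 4.40 |

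Each printed RBF is below the RPF of 763.

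**Reversal.** Take two participants with equal MAP and RPF and Hct of 0.44 and 0.39. The RVR ratio is 0.61/0.56 = 1.089 as printed and 0.56/0.61 = 0.918 when correct. That is 9% higher against 8% lower.

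**R_E as bracketed.** Read literally, R_E rises with flow and has the wrong units. On that reading the RBF error lowers it: at Hct 0.40 and FF 0.177 the factor is (0.60 − 0.177)/(1.667 − 0.177) = 0.28. R_E is wrong on either reading.

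**C_M row.** The term is printed as the log of 1/1-FF. Taken literally that is 1 − FF = 0.823, whose log is −0.195, so C_M would be negative. The intended ln(1/(1 − FF)) is +0.195.

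**Effect on a correlation (all inputs assumed).** Let Hct have mean 0.41 and SD 0.035, and let ln(MAP/RPF) have SD 0.2 and be unrelated to copeptin and Hct.

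- The SD of ln(1 − Hct) is about 0.035/0.59 = 0.059.
- The SD of ln(RVR) is √(0.04 + 0.0035) = 0.209.
- A copeptin–Hct correlation r gives a copeptin–ln(RVR) correlation of about ±0.059r/0.209 = ±0.28r.
- For r from 0.2 to 0.4, that is +0.06 to +0.11 as printed and −0.06 to −0.11 when correct.

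**The case against.** The best counter-argument is that a slash was lost when the table was read from PDF. Every other product in Table 3 carries an explicit multiplication sign, and only the RBF row has none. This cannot be excluded, so the sponsor should look at the source table. Against it, slashes survived in the FF, RVR, filtration-pressure, C_M, R_A and R_E rows, and the text as available reads as a product.

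The R_E and C_M rows may be loose shorthand. The investigators report using the Gomez equations before (Preliminary Studies, item 6), so their code may already be right. That is possible but cannot be seen from the documents. Table 3 is the only prespecified definition, and a programmer who follows it gets impossible values.

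The limits on reach stand in full. GFR, ERPF, FF, filtration pressure and P_GLO do not use RBF. The primary outcomes, hyperfiltration groups and power statements are therefore untouched by the RBF error. R_A and R_E are not named in Table 2.

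The limits on size also stand. A spurious correlation of 0.06 to 0.11 is small beside the 0.38 the study is powered to detect for GFR and ERPF. On the same assumptions, printed and correct ln(RVR) correlate at (0.04 − 0.0035)/(0.04 + 0.0035) = 0.84. Sex is already a candidate covariate. These points limit the consequence but do not make the formula right.

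**Conclusion.** Table 3 is wrong as written. The RBF error follows from the definition of haematocrit, and its direction for RBF, RVR and R_A holds at any haematocrit between 0 and 1. Over an assumed Hct of 0.35 to 0.45, RVR and R_A are overstated 2.4 to 3.3 times. R_E, read as a quotient at FF 17.7%, is overstated 2.9 to 4.4 times.

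The absolute values would be uninterpretable and not comparable with other published resistances. The haematocrit-driven part of any association would have the wrong sign. How far this distorts the copeptin correlations rests on assumed inputs and is probably modest. The damage is confined to one named secondary outcome and two derived resistances under H1.2.

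**What to change.** In Table 3:

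- Write RBF = RPF/(1 − Hct).
- Write R_E = [GFR/(K_FG × (RBF − GFR))] × 1328.
- Bracket the logarithm in the C_M row as ln(1/(1 − FF)).

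Check the source table for a lost slash, and check the analysis program against the corrected rows before RVR, R_A and R_E are computed. If any values already exist, recompute them. A simple program check is that RBF exceeds RPF for every participant.

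The cost is a text correction and a code check. Haematocrit, MAP, GFR and ERPF are already collected, so no new data, visits or participants are needed.
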